8. DATA ANALYSIS

8.1. Sample Size Determination

55 subjects will be enrolled to account for dropout. Standard deviation of the average plaque scores is assumed to be 1, with a correlation of 0.5 between the two study arms. With a minimum completed

test sample size of 45 subjects, the study will have 90% power to detect a difference of 0.5 between the average plaque scores with and without enzyme after waterjet, assuming a two-sided paired t-tests conducted at a two-sided 5% significance level.

8.2. Statistical Analysis

Intra-examiner repeatability of the individual surface scores will be evaluated using weighted kappa statistics and repeatability of the subject-level index scores will be evaluated using intra-class correlation coefficients (ICCs) and Bland-Altman plots. Subject-level plaque scores will be summarized by treatment (with or without enzyme) and stage (baseline, post-rinse, post-brushing, post-waterjet). The effects of the treatment will be evaluated using a repeated measures ANOVA suitable for a crossover study. The ANOVA will include fixed effects for treatment, stage, and their interaction, will treat stage as a repeated factor within subject for each study arm, and will include a factor for study arm. Age and sex groups will be included as covariates due to the stratified randomization. The ANOVA will also include an effect for treatment sequence to evaluate the model for a carry-over effect. If the treatment sequence effect is significant, the full analysis may need to be interpreted cautiously or the analysis may need to be limited to using only the results from the first study arm. A 5% significance level will be used for all tests. Statistical analyses will be performed using SAS version 9.4 (SAS Institute, Inc., Cary, NC).

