1. STUDY OBJECTIVE AND RATIONALE

1.1 Objective

The objective of this study is to determine if residual dental plaque following brushing can be mitigated by pre-rinse with broad spectrum oral proteolytic enzyme rinse and subsequent oral pulsating waterjet appliance, enhancing the oral hygiene of patients receiving orthodontic treatment.

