1.2. RATIONALE

Since the advent of modern orthodontic treatment, maintaining optimal oral hygiene has been troublesome for both the patient and the clinician. Fixed orthodontic appliances in the oral cavity are a physical barrier which can interfere with optimal oral hygiene. The tooth surface beneath the wire and adjacent to the orthodontic bracket are challenging areas for the patient to properly clean. The placement of this hardware creates obstructions and obstacles to the abrasive function of the toothbrush bristles. Poor removal of plaque adjacent to the brackets often leaves a visible halo or shadow effect on the tooth surface when the orthodontic hardware is removed. This discoloration halo (white spot lesion) is due to acidic demineralization of the tooth surface beneath the adherent dental plaque. The tooth surface beneath the bracket is protected from plaque development and resultant acidic leaching of dental minerals. Upon bracket removal, the discrepancy in tooth mineralization between these adjacent areas is now exposed creating the unaesthetic white spots. Unfortunately, many orthodontic patients to some degree, develop these unaesthetic white spots on their teeth.

The purpose of this research study is to determine if utilizing a proteolytic oral pre-rinse can hydrolyze the glycoprotein bonds which adheres the dental plaque to the dental pellicle (tooth surface in vivo). It is proposed here that the proteolytic enzyme may loosen the bond enough to allow for dislodgement by standard brushing, and further reduction in oral plaque with subsequent water jet propulsion.

The question to be answered is thus: in an adolescent patient with orthodontic appliances and poor oral hygiene, can the water jet more easily reach those areas protected from the bristles of the toothbrush (created by the orthodontic hardware) and dislodge the enzymatically loosened plaque? If so, an enzyme pre-rinse may have a place in orthodontic hygiene procedures.

The findings of this study may lead to future research studies investigating whether the addition of proteolytic enzymes can also enhance the overall oral hygiene in the general population. Possibly removing plaque between teeth and other areas where brushing alone can't reach.

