2. STUDY DESIGN

This will be a single site, cross-over, double-blind study with up to 55 subjects enrolled in the study. Since each person varies with technique and diligence in brushing their teeth, each subject will serve as their own control in this cross-over study. There will be at least a week time interval between the two arms of the study (length of wash out phase: one week). The study will be completed over the course of two weeks. Each step in the protocol will be timed to reduce inter- and intra-subject variability. Toothbrushes used in the study will be uniform, a new tooth brush will be used at each arm of the study. All oral hygiene aids will be of the same brand to eliminate variability (eg: all toothbrushes will be of the same brand, all disclosing tablets of the same brand, etc). For standardization and optimal photography, the same type of cheek retractor and digital camera will be used for all subjects.

Hypothesis

Null: There is no statistically significant difference in visual plaque scores with or without use of a proteolytic enzyme rinse aid.

Alternative: There is a statistically significant difference in visual plaque scores with use of proteolytic enzyme rinse aid.

Product Description

This study will use bromelain as the proteolytic enzyme in the oral rinse. Bromelain is an enzyme naturally found in high concentration in the stem of pineapples. This proteolytic, proteindigesting enzyme breaks down (hydrolyzes) proteins by reducing large complex proteins into smaller peptides or individual amino acids (25). For this reason, bromelain is commonly used as a digestive aid, (in pill form) or (in powder form) as a meat tenderizer.

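### Section 8.2 does not name the post-waterjet enzyme-placebo contrast that section 8.1 powers, and the 8.1 calculation does not support 90% power for the treatment main effect

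*Combined protocol and SAP*

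**What the plan says.** Section 8.1 states that with 45 completers "the study will have 90% power to detect a difference of 0.5 between the average plaque scores with and without enzyme after waterjet". The test is a two-sided paired t-test at 5%, with SD 1 and correlation 0.5 between arms.

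Section 8.2 plans a repeated measures ANOVA for the crossover: "The ANOVA will include fixed effects for treatment, stage, and their interaction". Its summary sentence gives the levels as "stage (baseline, post-rinse, post-brushing, post-waterjet". On error control it says only "A 5% significance level will be used for all tests". It mentions neither the paired t-test nor the post-waterjet comparison.

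No other section fills the gap. The objective in 1.1 asks whether "residual dental plaque following brushing can be mitigated by pre-rinse with broad spectrum oral proteolytic enzyme rinse and subsequent oral pulsating waterjet appliance", which points to the waterjet step without defining an endpoint. The rationale in 1.2 asks whether the jet can "dislodge the enzymatically loosened plaque", but also proposes that "the proteolytic enzyme may loosen the bond enough to allow for dislodgement by standard brushing". The null hypothesis in section 2 names no stage: "There is no statistically significant difference in visual plaque scores with or without use of a proteolytic enzyme rinse aid".

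**The concern.** The sample size rests on one contrast, while the analysis section lists three kinds of test and ranks none of them. The treatment main effect, the treatment-by-stage interaction or the post-waterjet contrast could each be reported as the trial's result, and they can disagree on the same data. The choice could then be made after the results are seen.

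The main effect is the term a reader would most easily take as the answer to the section 2 hypothesis. Under section 2.1 the first photograph at each visit is taken before the rinse. Absent carry-over, the true treatment difference at that stage is therefore zero, and a four-level main effect averages that zero in. It estimates a different quantity from the one in 8.1, and the stated power does not transfer to it.

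**Working it through.** **Inputs from the documents.** From 8.1: difference 0.5 after the waterjet, SD 1, correlation 0.5, 45 completers, two-sided 5%. From 8.2: four stages.

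**Inputs assumed.** The documents give no treatment effect at the earlier stages, no SD of the treatment difference at those stages, and no correlation c between stage differences. I take SD 1 at every stage, a common c from 0 to 0.9, and three effect profiles.

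**Step 1: reproduce 8.1.** SD of the paired difference = sqrt(2 × 1² × (1 − 0.5)) = 1. Noncentrality = 0.5 × sqrt(45) = 3.354 on 44 df. Power = 90.7% (90.0% at n = 44). The plan's figure stands.

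**Step 2: what a four-stage main effect targets.** This step needs no SD or correlation. Order: baseline, post-rinse, post-brushing, post-waterjet.

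- Waterjet only: (0 + 0 + 0 + 0.5)/4 = 0.125
- Even build-up: (0 + 1/6 + 1/3 + 1/2)/4 = 0.25
- Full effect at all post-rinse stages: (0 + 0.5 + 0.5 + 0.5)/4 = 0.375

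**Step 3: power of that main effect.** The mean of four differences with SD 1 and correlation c has variance (4 + 12c)/16 = (1 + 3c)/4. Noncentrality = target × sqrt(45) / sqrt((1 + 3c)/4), with 44 df.

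| Profile (target) | c = 0 | 0.3 | 0.5 | 0.7 | 0.9 |
|---|---|---|---|---|---|
| Waterjet only (0.125) | 37.5% | 22.2% | 18.0% | 15.4% | 13.7% |
| Even build-up (0.25) | 90.7% | 66.3% | 54.6% | 46.2% | 40.0% |
| All post-rinse stages (0.375) | 99.8% | 94.6% | 87.5% | 79.8% | 72.5% |

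The main effect reaches 90% only for the third profile with c below about 0.43, or for even build-up with c below about 0.01. If the SDs at the three earlier stages are 0.75 to 1.25 times the post-waterjet SD, the ranges widen to 11-52%, 30-98% and 58% to over 99%.

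**Step 4: consequence of leaving the test open.** On the step 3 assumptions with equal SDs, the main effect and the post-waterjet contrast disagree on significance in 55-78%, 13-51% and 9-18% of simulated trials for the three profiles (40,000 trials per setting). With no true effect at any stage, at least one of main effect, interaction (multivariate test) or post-waterjet contrast is significant in about 11-13% of trials (20,000 per value of c).

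**Step 5: does naming the contrast secure the 90%?** Only with a suitable variance, and 8.2 does not state a covariance structure. Suppose the model pools variance over the four stages.

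- Earlier-stage SDs 0.75 times the post-waterjet SD: pooled variance = (3 × 0.5625 + 1)/4 = 0.672 against a true 1. Simulated type I error is about 10%.
- Earlier-stage SDs 1.25 times: pooled variance = (3 × 1.5625 + 1)/4 = 1.422. Type I error is about 2% and power about 82-83%.

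With a stage-specific variance, or post-waterjet data alone, step 1 applies.

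**Step 6: baseline as covariate.** If the baseline and post-waterjet differences have correlation c, the residual variance is 1 − c² on 43 df. Power is 90.6% at c = 0, 93.0% at 0.3 and 96.6% at 0.5. Simulation that includes chance baseline imbalance gives 89.9%, 92.4% and 96.3% (20,000 trials each).

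**The case against.** The strongest reply is that 8.1 already identifies the key comparison and 8.2 supplies the model that estimates it. Section 8.2 speaks of treatment effects in the plural, includes the interaction that makes stage-specific comparisons available, and never says that the main effect decides the trial. That is the most natural reading, and the model can produce the contrast. But it remains an inference. 8.2 neither names the contrast nor ranks it above the other terms, and section 2 and the rationale leave room for another stage.

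It can also be said that the four levels appear in the sentence on descriptive summaries, not in the ANOVA sentence. This stands as a condition: the dilution in step 2 holds if the ANOVA uses those four levels, which is the likelier reading.

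Three stronger conclusions are tempting, and the documents do not support them.

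- A reader might infer that the main effect has less than 90% power. That depends on undocumented stage effects and correlations, and some scenarios exceed 90%.
- A reader might infer that the sample size is wrong. It reproduces.
- A reader might infer that keeping baseline as a stage is an error or causes bias. It does not; it changes what the main effect measures.

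**Conclusion.** The point holds as a mismatch between the powered comparison and the analysis section. 8.1 supports 90% power for the post-waterjet contrast only, and 8.2 does not designate that contrast. The reduction of 0.5 to between 0.125 and 0.375 for the three profiles is arithmetic, conditional on four stage levels and no baseline effect. The power ranges of 14-38%, 40-91% and 73% to over 99% rest on the assumed SDs and correlations. They show that 90% cannot be carried over to the main effect, not that its power has any particular value. The plan is usable and the defect is cheap to remove, so it should be corrected before analysis.

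**What to change.** In 8.2:

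1. Name the enzyme-placebo contrast after the waterjet, from the crossover model and on the subject-level average score used in 8.1, as the single primary test at two-sided 5%. Label the treatment main effect, the interaction and the other stages secondary. If the sponsor means another test to decide the trial, 8.1 has to be recalculated for that test.
2. Estimate the contrast with a stage-specific (unstructured) variance, or from post-waterjet data alone.
3. Use post-rinse, post-brushing and post-waterjet as the outcome stages, with each visit's baseline score as a covariate. This is for precision only and brings no gain if baseline and post-waterjet differences are uncorrelated. If baseline stays as a stage, items 1 and 2 are sufficient.

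The cost is SAP wording, plus about one within-subject degree of freedom for the covariate. The baseline photograph is already taken and scored. Sample size, visits and procedures do not change.

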- 1. The subject will then be asked to use a water jet cleansing device (WaterPik). This will also

be timed (two minutes). The instructions given to the subject: "Use this Waterpik to clean around the brackets and under the wires as best you can". All Waterpik devices will be set at the same medium pulsating pressure.

- m. Fourth frontal photograph for this visit obtained (including another random serial identifying number unique for subject, stage and visit).
- n. Subject receives \$25 Visa gift card and dismissed.
- o. Subject (or guardian) is phoned later that day & questioned if they have any concerns or side effects. Subject & Guardian are reminded of phone number contact of student researcher.

Second Visit (1week later)

a. Each subject will repeat the procedure as described above on the subsequent visit (a-n) with the second (vial) oral rinse treatment (placebo or enzyme).

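### Section 8.2 fits one visit effect common to all four stages, so a visit effect that differs by stage would bias or blur the powered post-waterjet contrast; one extra model term removes this

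*Combined protocol and SAP*

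**What the plan says.** Section 8.2 plans a repeated measures ANOVA for the crossover. Its listed fixed effects are treatment, stage, treatment-by-stage, study arm, age group, sex and treatment sequence. On the visit it says that the model "will treat stage as a repeated factor within subject for each study arm, and will include a factor for study arm". In this sentence the arm is the visit: section 2 says "There will be at least a week time interval between the two arms of the study", and 8.2 itself speaks of falling back on the first arm if the sequence effect is significant. The sequence term is there to look for carry-over.

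Section 8.1 powers one stage. The claim is "test sample size of 45 subjects, the study will have 90% power to detect a difference of 0.5", and the difference is the one "between the average plaque scores with and without enzyme after waterjet". The assumptions are "Standard deviation of the average plaque scores is assumed to be 1, with a correlation of 0.5 between the two study arms", "assuming a two-sided paired t-tests conducted at a two-sided 5% significance level", and "55 subjects will be enrolled to account for dropout".

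Section 2.1 has the subject operate the waterjet at both visits, with the single instruction "Use this Waterpik to clean around the brackets and under the wires as best you can". Under 5.2 the device is locked away between the visits.

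**The concern.** The treatment effect may take a different value at each stage, but the visit effect may not. A common visit effect assumes that whatever changes between visit 1 and visit 2 moves the baseline, post-rinse, post-brushing and post-waterjet scores by the same amount. That need not be so. Baseline is plaque disclosed before any procedure, whereas the last stage depends on how well the subject handles a device that they are using in the study for the second time at visit 2. A practice effect would act mainly at that last stage.

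In that case the common term removes only part of the visit effect from the post-waterjet scores. If more completers took enzyme first, practice at visit 2 favours placebo and the enzyme effect is understated. If more took placebo first, it is overstated. If the orders are equal the estimate is unbiased, but the unremoved part inflates the residual variance. The sequence, age and sex terms do not help, because they are constant between a subject's two visits and cancel from the within-subject difference.

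**Working it through.** **Inputs from the documents (8.1).** SD 1, correlation 0.5 between visits, target difference 0.5, two-sided 5%, 45 completers of 55 enrolled (10/55 = 18.2% loss allowed).

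**Assumptions not in the documents.** A visit effect L that lowers post-waterjet scores at visit 2 and changes no other stage, with L = 0.25 or 0.5; the split of completers between the two orders, n1/n2; and the covariance among stages.

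**1. The plan's own figure.** The SD of the paired difference is sqrt(2 × (1 − 0.5)) = 1. Noncentral-t power at n = 45 for a difference of 0.5 is 90.7% (90.0% at n = 44). The stated 90% reproduces.

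**2. Bias formula.** For subject i at stage k let D = visit 2 minus visit 1, and let s = +1 if enzyme came second and −1 if first. Then E(D) = s·τ_k + π_k, with τ_k the enzyme-placebo difference and π_k the visit effect. Here π is −L at the waterjet stage and 0 elsewhere. With one common visit effect π̂ fitted, the estimate at the last stage is mean(s·D) − m·π̂, where m is the mean of s, of size (n1 − n2)/N. If the stages are exchangeable, π̂ estimates one quarter of the waterjet effect, so three quarters remains:

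size of bias = 0.75 × L × (n1 − n2)/N

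| Split of 45 | (n1 − n2)/N | L = 0.25 | L = 0.5 |
|---|---|---|---|
| 23/22 | 0.022 | 0.004 | 0.008 |
| 25/20 | 0.111 | 0.021 | 0.042 |
| 27/18 | 0.200 | 0.038 | 0.075 |
| 30/15 | 0.333 | 0.062 | 0.125 |

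For L = 0.5 the last three rows are 8%, 15% and 25% of the 0.5 target.

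**3. How far the 0.75 depends on the covariance.** The factor is 1 minus the weight of the waterjet stage in π̂. It is 0.67 if the visit differences follow an AR(1) pattern with correlation 0.5, and 0.47 if the post-waterjet SD is 0.8 of that at the other stages with exchangeable correlation 0.5. A larger post-waterjet SD raises it.

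**4. Standard error with equal orders.** The residual variance at the last stage becomes 1 + (0.75L)².
- L = 0.25: sqrt(1 + 0.1875²) = 1.017, and power goes from 90.7% to 89.7%.
- L = 0.5: sqrt(1 + 0.375²) = 1.068, and power goes from 90.7% to 86.7%. Simulation at 23/22 gave 87% against 91% with a stage-specific visit effect.

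**5. Error rates with unequal orders.** These come from simulation of the listed model (unstructured covariance, t reference, exchangeable stages).
- L = 0.25: type I error is near nominal up to 27/18 (about 5%).
- L = 0.5: see below.

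| L = 0.5 | 27/18 | 30/15 |
|---|---|---|
| Type I error, planned model | about 6% | 10 to 12% |
| Power, imbalance against enzyme | about 75% | about 63% |
| Power, imbalance in favour of enzyme | about 95% | 97 to 98% |
| Power with visit-by-stage, either direction | about 89% | about 87% |

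**6. How likely such splits are.** If each of 45 completers had a fair-coin order, 27/18 or worse would occur in about 23% of trials and 30/15 or worse in about 4%. Section 4.5 stratifies by sex and age but describes no blocking on order. Section 2.1 step f lets the subject choose the first vial, while 5.1 has a statistician's list decide.

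**7. After the change.** With a separate visit effect at each stage the bias is zero at every split, and the SE is 1/sqrt(45 × (1 − m²)): 0.149 at 23/22, 0.152 at 27/18 and 0.158 at 30/15. If there is no stage-specific visit effect, the planned model would give 0.149 at 23/22 and 0.155 at 30/15.

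**The case against.** The strongest reply is that L is conjecture. No document describes or sizes a learning effect. Section 3.2 does not exclude subjects who already use a waterjet, and 2.1 fixes the time, pressure and instruction at both visits. A different plaque level on the day could shift all four photographs together, which is what a common visit term absorbs. L = 0.5 would mean that a single two-minute use a week earlier lowers plaque as much as the hypothesised enzyme effect. All of this stands, and it is why L = 0.5 is shown only as an upper end.

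It also stands that the 0.75 factor is not general, and that under a list as in 5.1 the orders may be closer than a fair coin gives. Even with a fair coin, 77% of trials would be better balanced than 27/18.

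A further reply is that 8.2 is a summary and calls for an ANOVA suited to a crossover, which leaves room for more interactions. It does leave room. But 8.2 names the treatment-by-stage interaction explicitly and gives the visit only a single factor. Treating stage as repeated within each arm describes the correlation structure and does not supply a visit mean for each stage.

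A reader might infer that type I error is badly inflated in general. The figures do not support that: at 27/18 with L = 0.5 it is about 6% with a t reference (about 7% with uncorrected maximum-likelihood variances and a normal reference), and at near-equal orders it is nominal or below. Nor should the 75% and 63% be read as expected power. They apply only when the imbalance opposes the enzyme, and the opposite imbalance raises power.

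**Conclusion.** The gap is real and of modest expected size. As listed, the model does not remove a stage-specific visit effect from the contrast that 8.1 powers. If L is 0.25 or less, or the orders are close to equal, the consequence is small: a bias of at most about 0.02 up to 25/20 for L = 0.25, and a loss of 1 to 4 points of power near balance for L up to 0.5. It becomes material only when a large effect (L near 0.5) meets a clear imbalance (27/18 or worse). These figures rest on an assumed L, assumed splits, SD 1 and exchangeable stages.

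Two stronger conclusions are tempting and are not supported. One is that the sample size or the 90% power is wrong: it reproduces under its own assumptions and still holds, to within about a point at splits up to 27/18, once the term is added. The other is that the trial will have a waterjet learning effect: the procedures make one plausible, but the documents neither report nor quantify it.

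**What to change.** Add the visit-by-stage interaction to the fixed effects in 8.2, so that the visit effect is estimated separately at each stage. Alternatively, for the powered comparison, fit the crossover model (treatment, visit, sequence, subject) to the post-waterjet scores alone. Specify the choice before unblinding, because adding the term afterwards would look data-driven. It would also help to write visit in 8.2 where arm is used in that sense.

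The cost is 3 degrees of freedom and no change to data or procedures. If there is no stage-specific visit effect, the SE is unchanged at 23/22 (0.149 either way) and rises from 0.155 to 0.158 at 30/15.

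Separately, section 2.1 step f and section 5.1 must be reconciled on how vial order is set, since that determines how balanced the orders can be.
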